6. STUDY DESIGN

This is a Greek observational prospective study to evaluate the effect of a biphosphonate drug, Alendronate, on BMD in postmenopausal women for a total period of 12 months. This observational study will not alter the routine clinical management of patients and will comply with all applicable local regulations of Greece. The decision to treat the patient with Alendronate must be made independent of and prior to their enrollment in the study. It is expected that patients eligible to participate will receive their first prescription during their initial clinic appointment and thereafter once monthly along with local standard clinical care according to clinical judgment and international guidelines. Approximately 512 patients will be enrolled in the study. The first 512 patients that will attend the orthopaedic clinic of Larisa Public Hospital and will be deemed appropriate candidates for biphosphonates treatment will be eligible to participate in the study. Detailed data obtained as part of routine clinical practice will be collected at the initial visit directly from patients or through their past medical record. These will comprise of demographic patient data, medical condition, risk factors for osteoporosis, and comorbidities. It is anticipated that patients will return to the clinic every month to receive their Alendronate prescription and record protocol adherence. After the initial visit, information regarding Alendronate prescription and administration, concomitant medication use, and non-serious and serious ADRs will be obtained during monthly clinical visits and recorded for up to approximately 6 months after completion of the study, a period that is thought appropriate to document ADRs and serious ADRs.

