10. STATISTICAL CONSIDERATIONS

Study Outcomes:

The following outcomes are to characterize/estimate the effectiveness during the first 12 months of treatment with Alendronate.

Primary outcome:

- BMD change (%) at lumbar spine at 6,12 months of treatment measured by DXA

Secondary outcomes:

- the proportion of patients with severe osteoporosis experiencing one or more new vertebral and non-vertebral fragility fractures assessed by spine radiographs regardless of symptoms
- Compliance to therapy, self-reported by patients
- Days lost from work due to fracture-related back pain, self reported by patients

The following secondary outcomes are to characterize the safety of patients during the first 12 months of treatment with Alendronate and during the 6 month follow up period:

- the proportion of patients with ADR to Alendronate
- the proportion of patients with serious ADR to Alendronate

The Full Analysis Set will consist of all enrolled patients satisfying the inclusion/exclusion criteria that receive at least 46 doses - 96% of the 48 that ideally would receive during the study duration- and have a non-missing enrollment date. All analyses will be performed on this analysis set.

Subsets and/or Covariates:

The following variables will be collected at baseline, either directly as part of routine clinical practice, or from medical records when available:

Demographic patient data:

- Educational level
- Patient employment status
- Patient living situation (at home with spouse/family, at home with care/support, at home alone, nursing home)

Medical condition regarding osteoporosis:

- Body mass index (≤ 25 or > 25 kg/m²)
- Age at menopause
- Cause of menopause (natural onset, clinically/surgically induced)
- Height loss since maximal height
- Height loss in centimeters (cm)
- Previous fracture
 - Previous hip fracture
 - Previous vertebral fracture
 - Other previous fractures
- Previous hospitalization for osteoporotic fracture and/or surgical osteoporotic fracture treatment
- One or more falls experienced during the past 12 months
- One or more episodes of immobility experienced during the past 12 months
- Parent fractured hip
- Current smoker
- Former smoker
- Systemic glucocorticoid use
- Secondary osteoporosis
- Alcohol consumption
- Femoral neck BMD T-score
- Lumbar spine BMD T-score
- Total hip BMD T-score

Patient-related:

- Age (years)
- Age group (< 65, ≥ 65 to <75, ≥ 75 years)
- Time since Post Menopausal Osteoporosis (PMO) diagnosis

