11. SAFETY DATA SELECTION AND ADVERSE EXPERIENCE REPORTING

Adverse Drug Reaction

Definition of Adverse Drug Reaction: An Adverse Drug Reaction (ADR) is defined as an adverse event associated with a given medication at normal dosage. The definition of adverse events includes worsening of a pre-existing medical condition. Worsening indicates the pre-existing medical condition (eg, diabetes, migraine headaches, gout) has increased in severity, frequency, and/or duration, and/or has an association with a significantly worse outcome. A pre-existing condition that has not worsened during the study, and involves an intervention such as elective cosmetic surgery or a medical procedure while on study is not considered an adverse event. The Investigator should specify the date of onset, intensity, action taken with respect to Alendronate, corrective treatment/therapy given, outcome and his/her opinion as to whether there is a reasonable possibility that the Adverse Event was caused by Alendronate.

Lab, vital signs, or ECG abnormalities are to be recorded as adverse events only if they are medically relevant: symptomatic, require corrective treatment, lead to study drug discontinuation and/or fulfill a seriousness criterion. In that case the procedure imposed by the event of a serious adverse drug reaction (SADR) should be followed.

Reporting Procedures for Adverse Drug Reactions: The investigator is responsible for ensuring that all ADRs to Alendronate 70mg observed by the investigator or reported by the patient that occur after the first administration of Alendronate through the end of study and through the following 6 months are captured. The investigator must assess whether any adverse event is possibly related to Alendronate 70mg and if that is the case he should proceed by recording the ADR and assign the following ADR attributes:

- ADR diagnosis or syndrome(s), if known (if not known, signs or symptoms),
- Date(s) of onset and resolution,
- Severity, and
- Action taken.

Serious Adverse Drug Reaction

Definition of Serious Adverse Drug Reaction: A SADR is a serious adverse event that is considered related to the medicinal product. A serious adverse event is defined as an adverse event that meets at least 1 of the following serious criteria:

- fatal
- life threatening (places the patient at immediate risk of death)
- requires in-patient hospitalization or prolongation of existing hospitalization

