14. SUPPLEMENTARY MATERIAL

Data collected per visit

Data collection	Timing	Enrollment	Observation period	End of Study (12 months)	Follow-up period (6 months)
Informed Consent		X			
Demographics		X			
Patient-related conditions		X			
Medical History		X			
Prior and Current Medication Use		X	X	X	
Menopause History		X			
Alendronate Prescription		X	X	X	
Calcium and Vitamin D supplementation		X	X	X	
ADR		X	X	X	X
SADR		X	X	X	X
Discontinuation and Reasons for Discontinuation		X	X	X	

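### The ADR and serious ADR proportions are analysed only in women who received at least 46 of 48 doses, which leaves out every woman whose reaction ended treatment or was fatal before dose 46

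*Protocol*

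**What the plan says.** Protocol section 10 (Study Outcomes) lists two safety outcomes, "the proportion of patients with ADR to Alendronate" and "the proportion of patients with serious ADR to Alendronate". They are meant to describe the "safety of patients during the first 12 months of treatment with Alendronate and during the 6 month follow up period".

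The next paragraph defines the only analysis set in the protocol, the Full Analysis Set. It holds enrolled, eligible women with a recorded enrolment date "that receive at least 46 doses - 96% of the 48 that ideally would receive during the study duration". It closes with "All analyses will be performed on this analysis set". There is no exception for safety.

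Other sections bear on the point:

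- Section 4 sets the safety objective as the kind, frequency and severity of ADRs over 18 months.
- Section 11 makes the investigator responsible for seeing that ADRs which "occur after the first administration of Alendronate through the end of study and through the following 6 months are captured". It names fatal outcome as a seriousness criterion and foresees events that lead to stopping the drug.
- Section 8 allows information to be collected after a woman has stopped treatment.
- The data-collection table in section 14 ticks ADR and SADR in every period. It ticks "Discontinuation and Reasons for Discontinuation" through month 12.
- Section 9 says that data gathered before a woman withdraws consent enter the analysis.

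**The concern.** Membership of the analysis set depends on the outcome that the set is used to measure. An adverse reaction is one of the main reasons why a woman might stop a drug, and a woman who stops early cannot reach 46 doses. The plan thus collects the reactions that matter most for tolerability, those that end treatment or life, and then leaves the women concerned out of both safety proportions.

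At stake is what the study will say about the safety of the drug in this population. A reader of the results would take the ADR proportions as describing women who start Alendronate. They would in fact describe women who tolerated it, and kept to it almost perfectly, for most of a year.

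**Working it through.** **1. The threshold.** 46/48 = 0.958, which reproduces the stated 96%. A woman may miss at most 2 of the 48 doses. On weekly dosing, dose 46 comes no earlier than 45 weeks after the first dose. Any reaction that ends treatment before then puts her outside the set for the whole 18 months.

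**2. What follows without any assumption.** If an ADR ends treatment or is fatal before dose 46, the woman is in neither numerator nor denominator. The contribution of such ADRs to both proportions is 0, whatever their true frequency.

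**3. The overall ADR proportion.** Let p be the true proportion among treated women, a the share of women with an ADR who reach 46 doses, and b the share of ADR-free women who do. Then

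reported = p·a / (p·a + (1 − p)·b).

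This is below p when a < b, equal to p when a = b, and above p when a > b. Only the ratio a/b matters, so losses that strike both groups equally cancel. The documents give neither p, a nor b, so the values below are assumptions.

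| True p | a/b = 0.75 | a/b = 0.50 | a/b = 0 |
|---|---|---|---|
| 5% | 3.8% | 2.6% | 0% |
| 10% | 7.7% | 5.3% | 0% |
| 20% | 15.8% | 11.1% | 0% |

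Example: p = 10% and a/b = 0.50 gives 0.05/(0.05 + 0.90) = 5.3%.

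**4. The same effect seen from adherence.** Assume ADRs in 5% of women who reach 46 doses and in 30% of the others. The plan reports 5% in each case.

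- If 90% reach 46 doses: true = 0.9 × 5% + 0.1 × 30% = 7.5%, a ratio of 1.5.
- If 60% reach 46 doses: true = 0.6 × 5% + 0.4 × 30% = 15%, a ratio of 3.

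The 90% case matches the only attrition figure in the protocol, the 10% allowance for loss in the sample size. That allowance is for lost subjects, not for women who miss more than two doses, so the share below 46 doses may be larger.

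**5. Section 9 against section 10.** For a woman who withdraws consent before dose 46, section 9 includes her data up to that date and section 10 excludes her. Nothing says which prevails. For a woman who only stops the drug, or who dies, consent has not been withdrawn. Section 9 does not reach her, and section 10 excludes her.

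**The case against.** Five points can be made on the other side.

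- **Section 9 already includes withdrawers.** This stands in part. The protocol contradicts itself for them, so it would be too strong to say that no early stopper can ever appear. On a broad reading, the mention of women unable to go on with the study might reach further. But the sentence concerns withdrawal of consent, and section 8 treats stopping the drug as something after which data may still be collected.
- **Downward bias is not guaranteed.** This stands for the overall proportion. The rule also removes ADR-free women who miss doses for other reasons. With p = 10%, a = 80% and b = 60% (assumed), the reported value is 0.08/(0.08 + 0.54) = 12.9%, above the truth. Downward bias is the likelier direction because reactions prompt stopping, but it does not follow from the definition alone.
- **Fatal and serious reactions are not lost.** This stands. A reader might infer that a fatal reaction vanishes from reporting. It does not: section 11 has serious ADRs entered in the medical record, the report form and the eCRF and reported to the national authority, and section 12 has serious events notified to the ethics committee. Only the analysed proportions are affected.
- **ADRs in months 13 to 18 can be related to exposure.** A reader might infer the opposite from the section 14 table, which leaves Alendronate prescription and medication use unticked in the follow-up column. But section 6 says that "information regarding Alendronate prescription and administration, concomitant medication use, and non-serious and serious ADRs will be obtained during monthly clinical visits" and recorded for about 6 months after completion, and section 11 asks for onset date and what was done about Alendronate. What remains is a minor mismatch between text and table.
- **These are secondary, descriptive outcomes of an approved drug, and a statistical analysis plan may exist.** True, but the protocol does not leave the set open. It fixes it for all analyses, and an analysis plan that followed it would carry the error forward.

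**Conclusion.** The point holds for the analysed ADR and serious ADR proportions. That reactions ending treatment or life before dose 46 contribute zero follows from the set definition and rests on no assumption, except that section 9 leaves the position unresolved for women who withdraw consent.

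The effect on the overall ADR proportion is probably downward. Its size cannot be derived from the documents. Under the assumed 5% and 30% ADR rates, the understatement is 1.5-fold if 90% reach 46 doses and threefold if 60% do. The threefold figure should not be read as an estimate for this study, and a claim that the proportions must be too low goes further than the documents support. The conflict with section 9 is a second, separate reason to correct the text.

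**What to change.** 1. In section 10, limit the sentence "All analyses will be performed on this analysis set" to the effectiveness outcomes at most.
2. Define a safety set of all enrolled women who take at least one dose of Alendronate. Use it for both ADR outcomes, from first dose to the end of the 6-month follow-up.
3. Report the number and proportion of women who discontinue because of an ADR.
4. Reconcile section 9 with section 10, so that the text says in which analyses data from women who withdraw consent before dose 46 are used. State also how women who stop the drug or die are handled.
5. Minor: align the follow-up column of the section 14 table with section 6 on prescription and medication use.

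The cost is wording only. ADRs are already to be captured from the first administration and reasons for discontinuation are already scheduled, so no extra patients or procedures are needed. The reported ADR proportions may be less favourable.

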- Number of comorbidities
- Any chronic medical condition
- Type of chronic medical condition (diabetes/osteoporosis/hypertension/other)

Sample Size:

A review of published data highlighted that BMD change at lumbar spine at 12 months for postmenopausal women on alendronate 70mg weekly ranges from 3.7%-5.1%.¹³⁻¹⁵

Taking into account the most unfavourable result, which is 5.1%, we will estimate the sample size of our study. We will conduct an observational study which intends to investigate the Lumbar Spine BMD (%) change from baseline to 12 months (single proportion).

Published data estimate that Lumbar Spine BMD increases 5.1% from baseline to 12 months.

We would like to ensure that 95% CI of the Lumbar Spine BMD change (%) is estimated with precision ±2% (i.e. with a margin of error of 2%).

The required sample size would be $n \geq \frac{z^2}{\delta^2} p(1-p) \rightarrow n \geq \frac{1.96^2}{0.02^2} 0.051(1-0.051) \rightarrow n \geq 465$

If we add 10% to compensate for potential loss of subjects, the final number will sum up to $n \geq 512$ patients.

Thus in order to have sufficient precision and compensate for potential loss of subjects the final sample size should be 512 patients.

Data Analyses

This is an observational study for which the analysis will be descriptive in nature and no formal hypothesis will be tested. T test will be used to assess the change in BMD between baseline and end of study measurements. Significance was indicated at $P < 0.05$.

For quantitative parameters (BMD, days lost from work) mean, standard deviation, median, range (minimum and maximum), as well as number of missing data (if relevant) will be displayed. For qualitative parameters (bone fractures) counts, percentages and number of missing data if relevant will be displayed. Treatment compliance for each patient will be calculated as the number of doses study drug was actually taken, with the maximum count being 48. Compliance will be regarded as a quantitative parameter.

In general, missing values will remain as missing, i.e., no attempt will be made to impute missing values and only observed values will be used in data analyses and presentations.

Baseline characteristics will be described. Demographics, medical history and other baseline variables will be summarized as appropriate to the type of data.

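### The sample size treats the mean percent change in lumbar spine BMD as a single proportion, so 465, 512 and the ±2% precision do not describe the primary outcome

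*Protocol*

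**What the plan says.** Protocol section 10 (Study Outcomes) defines the primary outcome as "BMD change (%) at lumbar spine at 6,12 months of treatment measured by DXA".

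Under Sample Size, the same section reports from the literature that "BMD change at lumbar spine at 12 months for postmenopausal women on alendronate 70mg weekly ranges from 3.7%-5.1" percent. It then chooses the upper end: "Taking into account the most unfavourable result, which is 5.1%, we will estimate the sample size of our study". The quantity is labelled a proportion: "We will conduct an observational study which intends to investigate the Lumbar Spine BMD (%) change from baseline to 12 months (single proportion"). The precision target is "We would like to ensure that 95% CI of the Lumbar Spine BMD change (%) is estimated with precision ±2" percent. The formula is z²p(1−p)/δ² with z = 1.96, p = 0.051 and δ = 0.02, which gives n ≥ 465. A 10% addition brings this to 512.

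Under Data Analyses, the same variable is treated as continuous: "For quantitative parameters (BMD, days lost from work) mean, standard deviation, median, range", with counts and percentages kept for qualitative parameters such as fractures. The change from baseline is assessed by a t test.

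The Synopsis ties 512 to reaching the desired precision. Sections 6 and 7 repeat the number.

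**The concern.** The variance p(1−p) belongs to a yes/no outcome, where p is the share of patients with the event. Here 5.1% is an average gain in bone density. It is not a share of women, and the protocol defines no BMD responder that would turn it into one. The width of a confidence interval for a mean depends on the SD of the individual changes and on the number of women analysed. It does not depend on the mean itself. The SD is the one input the calculation needs, and it is absent.

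At stake is the protocol's only quantitative justification for its size. Ethics committees and readers are told that 512 women are needed for a stated precision, and neither the number nor the precision has been derived for the primary outcome.

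**Working it through.** **Inputs.** From Protocol section 10: z = 1.96, p = 0.051, δ = 0.02, published range 3.7% to 5.1%, loss allowance 10%. The SD of the percent change is not given, so it is an assumption below.

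**Step 1: reproduce the protocol's figures.**
- n = 1.96²/0.02² × 0.051 × 0.949 = 9604 × 0.0484 = 464.8, so 465.
- 465 × 1.10 = 511.5, so 512.

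Both figures reproduce. There is no slip in the arithmetic.

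**Step 2: find the SD that the formula implies.** Setting z²p(1−p)/δ² beside the formula for a mean, (z × SD/δ)², shows that p(1−p) stands in for SD². Then √(0.051 × 0.949) = 0.220, an SD of 22.0 percentage points. That value is fixed by the mean and not by any data on spread.

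**Step 3: see why 5.1% is called unfavourable.** With p = 0.037 the same formula gives 9604 × 0.037 × 0.963 = 342.2, so 343. The required n rises with p because p(1−p) does. That is the only sense in which the largest published gain is the worst case. For the mean of a continuous outcome this dependence disappears.

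**Step 4: apply the formula for a mean.** n = (1.96 × SD/2)², and half-width at 465 evaluable women = 1.96 × SD/√465, both in percentage points:

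| Assumed SD | n for ±2 points (normal) | n for ±2 points (t-based) | Half-width at 465 evaluable |
|---|---|---|---|
| 3 | 9 | 12 | 0.27 |
| 5 | 25 | 27 | 0.45 |
| 8 | 62 | 64 | 0.73 |
| 10 | 97 | 99 | 0.91 |
| 20 | 385 | 387 | 1.82 |
| 22 | 465 | 468 | 2.00 |

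The break-even SD at 465 evaluable women is 2 × √465/1.96 = 22.0 points. Below it, the interval is narrower than ±2.

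**Step 5: vary the number analysed.** Section 10 limits all analyses to women with at least 46 of 48 doses and uses observed values only, so 465 evaluable women cannot be taken for granted. As an illustration, suppose half of 512, that is 256, were evaluable. The half-width would be 1.96 × SD/16, or 0.37 points at SD 3 and 0.98 at SD 8. The break-even SD would be 2 × 16/1.96 = 16.3 points.

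**The case against.** No defence of the formula itself was found. The outcome definition, the planned summaries and the t test all treat BMD change as continuous. An unseen SAP would not cure it, because the protocol states the formula and its result outright.

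The best counter-argument concerns consequences. The planned analysis does not use p(1−p), so the BMD estimate and its interval would be unaffected. The likely error is too many women rather than too few, in a study that supplies no treatment and adds no procedures (section 8). That stands, and it limits the harm, but the stated justification is still wrong.

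A reader might infer more than the documents support:

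- **That ±2 points would be nearly uninformative.** It would not separate values within 3.7% to 5.1%, but the protocol does not set out to do so. Even 3.7 ± 2 runs from 1.7 to 5.7 and excludes zero.
- **That the cohort's precision is known to be several times better than stated.** This depends on an assumed SD and on how many women are analysable. The half-widths above are illustrations.
- **That the loss allowance is a further error.** The text says "If we add 10% to compensate for potential loss of subjects, the final number will sum up to" 512, and adding 10% does give that. Dividing by 0.90 would give 517, a different convention with an immaterial effect here.
- **That the fracture outcome could justify 512 instead.** That outcome is restricted to women with severe osteoporosis, a subgroup of unstated size, so 465 is not its denominator.

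**Conclusion.** Wrong as written. The figures 465 and 512 and the ±2% margin are correct arithmetic for a yes/no outcome with a frequency near 5.1%, which is not the primary outcome. For the mean percent change in BMD they rest on an implied SD of about 22 points that the protocol neither states nor supports.

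If the SD is 3 to 8 points (an assumption), ±2 points needs about 9 to 62 evaluable women, so 512 probably exceeds what the stated precision requires. At 465 evaluable women that direction holds for any SD below about 22 points. A reader might conclude that the study is too small for its primary outcome; nothing in the documents points that way.

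**What to change.** In Protocol section 10, Sample Size:

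1. Replace the formula with n = (1.96 × SD/δ)². Give the SD of the 12-month percent change with its source, and a margin δ justified on the BMD scale.
2. Delete the single-proportion label and the description of 5.1% as the most unfavourable result.
3. State the expected half-width for the number of women expected in the analysis set, meaning those with at least 46 doses and an observed 12-month BMD.
4. Align the Synopsis sentence that ties 512 to the desired precision, and check the repeats of 512 in sections 6 and 7.

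Enrolment can remain at 512 in either of two ways. One is to say plainly that it exceeds the need for the primary mean. The other is to support it by the expected precision for the ADR proportion, a genuine proportion listed among the safety outcomes, with the assumed rate declared as an assumption.

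The cost is a rewritten sample size paragraph and consistent wording in the places that repeat the number. Data collection and the planned analysis do not change.

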9. REMOVAL AND REPLACEMENT OF PATIENTS

Removal of Patients:

Patients have the right to withdraw fully from the study at any time and for any reason without prejudice to her future medical care by the physician or at the institution. Withdrawal of full consent for this study means that the patient does not wish to or is unable to continue further study participation; patient data up to withdrawal of consent will be included in the analysis of the study. The investigator will discuss with the patient appropriate procedures for withdrawal from the study. Should a patient (or a legally acceptable representative) request or decide to withdraw from the study, all efforts will be made to complete and report the observations as thoroughly as possible up to the date of withdrawal. All information should be reported on the applicable eCRFs.

Replacement of Patients:

Participants who withdraw from the study or lost to follow-up will not be replaced.

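### Enrolling 512 does not secure the 465 analysed women behind the precision claim, because the 10% allowance covers loss of subjects but neither the 46-dose rule nor missing paired scans

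*Protocol*

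**What the plan says.** **Sample size (protocol, Section 10).** The planning value is stated as "Published data estimate that Lumbar Spine BMD increases 5.1% from baseline to 12 months". The target is "We would like to ensure that 95% CI of the Lumbar Spine BMD change (%) is estimated with precision ±2" percent, and the method is a single-proportion formula, which gives 465. The protocol continues "If we add 10% to compensate for potential loss of subjects, the final number will sum up to" 512, and concludes: "Thus in order to have sufficient precision and compensate for potential loss of subjects the final sample size should be 512 patients".

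**Analysis set (Section 10, Study Outcomes).** The Full Analysis Set is made up of eligible enrolled women who "receive at least 46 doses - 96% of the 48 that ideally would receive during the study duration- and have a non-missing enrollment date". It is the only set defined, and every analysis is to be run on it.

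**Missing data (Section 10, Data Analyses).** Nothing is imputed and only observed values are used.

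**Replacement and withdrawal (Section 9).** "Participants who withdraw from the study or lost to follow-up will not be replaced". The same section says that a woman's data up to the point where she withdraws consent are to enter the analysis.

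**The concern.** The 465 is a number of women analysed, and 512 is a number enrolled. The 10% step has to cover everything that separates the two, yet it is justified by loss of subjects alone. The protocol itself creates two further exits from the primary analysis:

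- women who stay in the study but fall below 46 doses;
- women without both a baseline and a 12-month scan.

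Neither has an expected rate or an allowance. The second exit is a real possibility on the protocol's own text. Section 7 admits women on a low-intensity fracture without a qualifying DXA result, Section 8 requires no assessments beyond routine care, and the visit table in Section 14 has no DXA row.

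What is at stake is the statement that 512 gives sufficient precision. It is made for a number that the plan has not shown it will analyse, and without replacement a shortfall cannot be made good during the study.

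**Working it through.** **Inputs.** From the protocol: p = 0.051, margin 0.02, z = 1.96, 10% allowance, 512 enrolled, dose rule 46 of 48. Not in the protocol, so assumed as ranges: the share of retained women meeting the dose rule, and the SD of the % BMD change.

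**1. The plan's own figures reproduce.**
- 1.96² × 0.051 × 0.949 / 0.02² = 464.8, so 465.
- 465 × 1.10 = 511.5, so 512.

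**2. What 512 can absorb.**
- 512 − 465 = 47 women, and 47/512 = 9.2%, from all causes together.
- A 10% loss leaves 512 × 0.90 = 460.8, about 461.
- To keep 465 after a 10% loss, the division is 465/0.90 = 516.7, so 517.
- Alone, this step is trivial: 1.96 × √(0.051 × 0.949/460.8) = 2.01%, against 2.00% at 465. Its relevance is that nothing is left over for the other exclusions.

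**3. Adding the dose rule (share meeting it is assumed).** Analysed n = 512 × 0.90 × share. Relative interval width = √(465/n), which holds for a mean or a proportion.

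| Share of retained women meeting the rule | Analysed n | Width relative to n = 465 |
|---|---|---|
| 100% | 460.8 | 1.005 |
| 90% | 414.7 | 1.06 |
| 80% | 368.6 | 1.12 |
| 70% | 322.6 | 1.20 |

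Missing paired scans would lower these numbers further. No rate is given for them either.

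**4. What this means for ±2 points.** The primary outcome is a mean percentage change, summarised with mean and SD and tested with a t test. Using p(1 − p) as its variance implies an SD of √(0.051 × 0.949) = 0.22, that is, 22 percentage points. For a mean, the half-width is 1.96 × SD/√n:

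| Analysed n | SD 3 (assumed) | SD 5 (assumed) | SD 10 (assumed) | SD 20 (assumed) |
|---|---|---|---|---|
| 460.8 | 0.27 | 0.46 | 0.91 | 1.83 |
| 414.7 | 0.29 | 0.48 | 0.96 | 1.92 |
| 368.6 | 0.31 | 0.51 | 1.02 | 2.04 |
| 322.6 | 0.33 | 0.55 | 1.09 | 2.18 |

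At 322 analysed, ±2 points is still met for any SD up to 2 × √322/1.96 = 18.3, about 18 points.

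**5. Sections 9 and 10 side by side.** Section 9 promises that data up to withdrawal will be used. Section 10 confines all analyses to women with at least 46 doses, so a woman who withdraws before reaching 46 doses contributes to no analysis. The two statements cannot both apply to her.

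**The case against.** A reader might infer that 512 will fail to give 465. The documents do not show that. They give no adherence rate, and 465 is reached if all exclusions together stay at or below 47 women (9.2%). Loss of subjects is not defined either, and could be read to include women lost to the analysis set. This stands: the claim is unsecured, not refuted. Even on that wide reading, though, a full 10% exclusion leaves 461.

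The dose rule may also bite less than it seems. The analysis set speaks of doses received, whereas compliance is counted in doses actually taken, and women attend monthly to receive a prescription. If receiving means being prescribed, most women who complete their visits would qualify. The text does not settle this, so the shares in the working are assumptions.

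The strongest objection is that 465 is the wrong benchmark. It comes from a proportion formula applied to a mean. A reader might infer that the ±2 target is in danger, or that every interval will be wider than planned. For the primary outcome neither follows: with an SD up to about 18 points, the interval for the mean stays within ±2 even at 322 analysed. That stands in full and limits the severity. It does not remove the mismatch, because a size recalculated for a mean would still have to be inflated for the set actually analysed.

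**Conclusion.** The point holds as a minor inconsistency. The stated enrolment is not matched to the stated analysis set: the single 10% allowance, if used up by loss, already leaves 461, and nothing is set aside for the dose rule or for missing paired scans. The arithmetic behind 465 and 512 is reproduced. What is unsupported is the step from 512 enrolled to 465 analysed.

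The size is unknown. After 10% loss, with an assumed 90% to 70% of retained women meeting the rule, about 414 to 322 are analysed, and intervals are about 6% to 20% wider than at 465. This rests on the 46-dose rule excluding some women who are not otherwise lost. It is not evidence that the study is too small for ±2 points on mean BMD change. That would need an SD above about 18 points at 322 analysed, and the protocol states no SD.

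**What to change.** Keep 512 enrolled and revise Section 10 as follows.

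1. In Sample Size, state expected loss and expected analysis-set exclusions (dose rule, missing paired scans) separately, and apply them by division: enrolled = analysed / evaluable fraction.
2. State the number expected to be analysed from 512, and drop the claim that 512 delivers 465 analysed.
3. Give the precision for a mean % change, 1.96 × SD/√n, with a stated SD or SD range and a short table over evaluable fractions. Do not build this table on the proportion formula, whose half-widths have no meaning for a mean.
4. Reconcile the 46-dose analysis set with the statement in Section 9 on data up to withdrawal, and say whether doses received means prescribed or taken.

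The cost is a few sentences and one small table, with no extra patients or procedures. The authors must commit to an expected evaluable fraction and an SD, and the number expected to be analysed may be stated as lower than 465.
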